## 10.3 Multi-center Trial Considerations

Up to 11 sites will participate in the study.

This is non-randomized, single arm, multi-center clinical study to assess safety and performance of Neqstent device with standardization of subject enrollment, data entry and AE reporting.

## 10.4 Endpoints

### 10.4.1 Primary Endpoints

#### **Primary Safety Endpoint:**

The proportion of subjects with death of any non-accidental cause or any major disabling stroke within the first 30 days after treatment or major disabling stroke or death due to neurological cause from day 31 to 6 months after treatment.

Note: Major Disabling Stroke is defined as an episode of neurological signs or symptoms that persist beyond 24 hours accompanied with evidence of ischemia/infarction on imaging that results in an increase of NIHSS from baseline by  $\geq 4$  points and/or an increase from mRS baseline by  $>2$ .

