**Table 1. Implant Size Selection Guide**

REF (Catalog Number) – Diameter	Aneurysm Neck (mm)
NQS407-XX – 7 mm	3.0 - 5.0
NQS409-XX – 9 mm	4.0 - 6.0
NQS411-XX – 11 mm	5.0 - 8.0

 Stryker Neurovascular Excelsior® XT-27® (0.027" ID, 2.9F/2.7F OD, 150cm Length)

 Detachable Coil Power Supply: Stryker Neurovascular InZone® Detachment System, REF M00345100940

 Power Supply Detachment Cable: Stryker Neurovascular IZDS Connecting Cable, REF 00345110250

Clinical Investigation Plan

Title

*Confidential & Proprietary*

**Coil Assisted Flow Diversion: A prospective, single arm, multi-center study to assess the safety and performance of Neqstent in adjunctive therapy (CAFI Study)**

Objective and Endpoints	
The primary objective of this study is to document the safety and performance of the Neqstent.
 
1. Primary Safety Endpoint:
 
The proportion of subjects with death of any non-accidental cause or any major disabling stroke within the first 30 days after treatment or major disabling stroke or death due to neurological cause from day 31 to 6 months after treatment.
 
Note: Major Disabling Stroke is defined as an episode of neurological signs or symptoms that persist beyond 24 hours accompanied with evidence of ischemia/infarction on imaging that results in an increase of NIHSS from baseline by <math>\geq 4</math> points and/or an increase from mRS baseline by <math>>2</math>.
 
2. Primary Performance Endpoint:
 
To demonstrate the occlusion rate on the 6 month angiogram as adjudicated by a core laboratory. Success will be defined as complete occlusion demonstrated by a Grade 1 using the Raymond Roy Scale.
 
Note: In the event of a Grade 2 or more using the Raymond Roy Scale, a second assessment will be made at 12 month follow-up to re-assess for remnant stability and/or complete occlusion and will be reported as a secondary efficacy endpoint.

Sample Size	51 subjects will be enrolled to obtain adequate follow-up data for the study to complete sponsor obligation to the notified body.
Number of Sites	Up to 11 sites will enroll in the study.
Study Visits	Baseline, procedure, discharge, one (1) month, six (6) months, twelve (12) months and twenty-four (24) months.

Clinical Investigation Plan

Title

*Confidential & Proprietary*

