## Clinical Investigation Plan

## Title

*Confidential & Proprietary*

**Coil Assisted Flow Diversion: A prospective, single arm, multi-center study to assess the safety and performance of Neqstent in adjunctive therapy (CAFI Study)**

Follow-Up and Required Assessments	All implanted subjects will complete the scheduled follow-up assessments. Adverse events will be collected from device implantation through study duration. Table 2 highlights the required assessments:							
	Table 2. Schedule of Assessments							
		Baseline#	Procedure	Discharge	1-month (± 1 weeks)	6 months (± 1 month)	12 months (± 1 month)	24 months (± 1 month)
Medical history and medications		X					X	
Neurologic Exam		X		X	X	X	X	
NIH Stroke Scale		X	X*	X*	X*	X*	X	X*
Modified Rankin Scale (mRS)		X		X**	X**	X**	X**	X**
Medical history and medications		X					X	
Neurologic Exam		X		X	X	X	X	X
NIH Stroke Scale		X	X*	X*	X*	X*	X	X*
Modified Rankin Scale (mRS)		X		X**	X**	X**	X**	X**
Pregnancy test (pre-menopausal female)		X						
CT angiography (CTA) ^		X #				X	X****	
Magnetic Resonance Angiogram (MRA) ^		X #						
Cerebral Angiogram (DSA) ^		X # w/3D	X w/3D			X w/3D	X*** w/3D	
Adverse Event assessment			X	X	X	X	X	X
Procedure Information			X					
Aneurysm Occlusion Status – Raymond Roy and general assessment on study form ##			X			X	X***	

^ Baseline image aneurysm assessment can be made with either CTA, MRA **OR** DSA, upon MD discretion.  
# Baseline image screening can be completed within 3 months prior to enrollment. Imaging will always be performed on the day of the procedure which will be used for core laboratory baseline for comparison at 6 months.  
\* The NIH Stroke Scale score should be obtained within 24 hours after stroke in the event a subject is diagnosed with a stroke.  
\*\* mRS will be obtained at all scheduled visits.  
\*\*\* Cerebral angiogram is required at 6 months only; in the event of a Grade 2 or more using the Raymond Roy Scale at 6 months, a second cerebral angiogram assessment will be made at 12-month follow-up to re-assess for complete occlusion and will be reported as secondary efficacy.  

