**Table 5. Risks of Endovascular Aneurysm Treatment**

Anticipated Risk	Percent Anticipated Risk Occurrence	Specified Risks
Neurovascular procedure related	Rarely (< 5%)	CVA – ischemic
	Rarely (< 5%)	CVA – hemorrhagic
	Rarely (< 5%)	Aneurysm rupture
	Rarely (< 5%)	Blood vessel dissection
	Rarely (< 5%)	Blood vessel perforation/rupture
	Rarely (< 5%)	Subarachnoid hemorrhage
	Rarely (< 5%)	Parenchymatous hematoma
	Rarely (< 5%)	Intraventricular hemorrhage
	Rarely (< 5%)	Thrombosis with resultant occlusion of aneurysm parent artery or other blood vessel
	Rarely (< 5%)	Embolism with resultant occlusion of blood vessel
	Less Likely (5-15%)	Device migration – from the aneurysm to a distal site
	Likely (>15%)	Headache
	Rarely (< 5%)	Cranial nerve palsy

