### 6.1.1 Risk Mitigation

The manners in which risks shall be minimized for the device procedure include the following:

1. The PI and clinical site staff were chosen because of their expertise in the field of neurovascular procedures.
2. The physician(s) performing device-related procedures have received the appropriate training in the use of the device.
3. Subjects are being monitored/observed throughout the study by multiple-disciplinary site staff, trained in the management of patients with IAs.

 Cerus Endovascular	Document Number DNQS428-01	Rev. F	Page 28 of 119
Clinical Investigation Plan	Title		
Confidential & Proprietary	Coil Assisted Flow Diversion: A prospective, single arm, multi-center study to assess the safety and performance of Neqstent in adjunctive therapy (CAFI Study)		

4. Extensive pre-clinical, bench and *in vivo* testing was performed in order to optimize the device safety and function.
5. Sponsor Clinical Personnel shall provide oversight throughout the Study.

Experienced Clinical Monitors will perform on-site and remote Monitoring throughout the trial to ensure protocol compliance and compliance with ISO 14155:2011 and all applicable EC and competent authority (CA) regulations. Neqstent is being designed and developed in accordance with a risk management process that conforms with EN ISO 14971:2012. This process serves to identify hazards associated with the subject devices and accessories, estimate and evaluate the risks associated with those hazards, control (reduce) those risks, and monitor the effectiveness of that control. Risk management ensures that risks to the patient, users and third parties are minimized and determined to be acceptable. The risk management results are crosschecked against applicable risk reduction documentation to ensure the risk reduction measures are implemented.

The Cerus Endovascular design review process ensures that all identified risk reduction measures have been implemented. Residual risks, the risks remaining after risk control (i.e. risk reduction) measures have been taken, are addressed in the “Contraindications” and “Adverse Events” sections of the Instructions For Use as well as listed in Table 5.

Potential adverse events associated with use of Neqstent, some of which could be fatal or cause severe neurologic deficits, include:

- Aneurysm rupture causing intracranial hemorrhage
- Injury to parent artery causing thrombosis or hemorrhage

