- Distal embolization of particles or blood clot causing stroke
- Parent artery vasospasm
- Parent artery dissection
- Aneurysm recanalization
- Infection
- Device migration causing incomplete occlusion, hemorrhage or ischemic stroke

Contraindications:

- Allergy to platinum, nickel or titanium

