**Table 8. Schedule of Assessments**

	Baseline #	Procedure	Discharge	1-month (± 1 weeks)	6 months (± 1 month)	12 months (± 1 month)	24 months (± 1 month)
Medical history and medications	X					X	
Neurologic Exam	X		X	X	X	X	X
NIH Stroke Scale	X	X*	X*	X*	X*	X	X*
Modified Rankin Scale (mRS)	X		X**	X**	X**	X**	X**
Pregnancy test (pre-menopausal female)	X						
CT angiography (CTA) ^	X #				X	X****	
Magnetic Resonance Angiogram (MRA) ^	X #						
Cerebral Angiogram (DSA) ^	X # w/3D	X w/3D			X w/3D	X*** w/3D	
Adverse Event assessment		X	X	X	X	X	X
Procedure Information		X					
Aneurysm Occlusion Status – Raymond Roy and general assessment on study form ##		X			X	X***	

^ Baseline image aneurysm assessment can be made with either CTA, MRA **OR** DSA, upon MD discretion.

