### Analysis Population

The safety population consists of all patients who are implanted with the study device. The primary analysis for all safety endpoints will be performed on this population.

The analysis for all primary and secondary study endpoints and baseline, procedural and follow-up characteristics will be performed on an intent-to-treat analysis population which will include all available data for all enrolled subjects. Standard summary statistics will be calculated for all study variables.

 Cerus Endovascular	Document Number DNQS428-01	Rev. F	Page 46 of 119
Clinical Investigation Plan	Title		
Confidential & Proprietary	Coil Assisted Flow Diversion: A prospective, single arm, multi-center study to assess the safety and performance of Neqstent in adjunctive therapy (CAFI Study)		

The primary safety endpoint will be calculated as the proportion of subjects with death of any nonaccidental cause or any major stroke within the first 30 days after treatment or major stroke or death due to neurological cause from day 31 to 6 months after treatment.

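### The stroke component of the primary safety endpoint requires ischemia or infarction on imaging, so a survived disabling intracranial hemorrhage without infarction is not counted

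*Combined protocol and SAP*

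**What the plan says.** Section 10.4.1 defines the primary safety endpoint as the proportion of subjects with non-accidental death or major disabling stroke up to day 30, or with major disabling stroke or neurological death from day 31 to 6 months. A note defines the stroke component as an episode of "neurological signs or symptoms that persist beyond 24 hours accompanied with evidence of ischemia/infarction on imaging" that leads to an NIHSS increase of at least 4 points and/or an mRS increase of more than 2. The synopsis (Section 2, Objective and Endpoints) carries the same condition: "accompanied with evidence of ischemia/infarction on imaging".

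Section 10.6 (Analysis Population) says how the endpoint will be calculated, in different words: "any major stroke within the first 30 days after treatment or major stroke or death due to neurological cause". The word *disabling* is missing, and *major stroke* is not defined in the text available.

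The plan expects that bleeding can occur. Table 5 lists "CVA – hemorrhagic" in its own row beside ischemic CVA, with further rows for aneurysm rupture, subarachnoid hemorrhage, parenchymatous hematoma and intraventricular hemorrhage. Section 6.1.1 lists potential adverse events, some of which it says could be fatal or leave severe neurologic deficits. They include "Aneurysm rupture causing intracranial hemorrhage" and "Device migration causing incomplete occlusion, hemorrhage or ischemic stroke".

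On measurement, the "NIH Stroke Scale" row of Table 8 marks the procedure, discharge, 1-month and 6-month visits as conditional. The footnote, which also appears under Table 2, reads: "The NIH Stroke Scale score should be obtained within 24 hours after stroke in the event a subject is diagnosed with a stroke". The mRS is scheduled at every visit.

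**The concern.** The device is placed in an aneurysm, and the plan names rupture and intracranial bleeding among the serious ways in which treatment can go wrong. A reader of a rate of death or major disabling stroke would normally take it to include a disabling hemorrhagic stroke, all the more because Table 5 itself classes hemorrhage as a type of CVA. As defined, the endpoint counts a bleed that kills (within the rules of the death component) and a bleed accompanied by infarction. It does not count a bleed that disables a survivor without infarction. The plan gives no reason for this.

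What is at stake is the content of the headline safety figure. Section 10.6 expects the 51 patients to give adequate evidence of safety for a pre-market study, and Section 12.1.15 sends the final report to the notified body. Section 10 says the study is not powered for significance and relies on clinical judgement, so the observed proportion carries much of the safety message.

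**Working it through.** The plan states no expected rate or threshold for the safety endpoint, so there is no figure of its own to reproduce. The sample size in Section 10.6 rests on success rates of 70% and 55% and is not affected.

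**Step 1: read the definition as a rule.** The conditions for major disabling stroke are:

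1. signs or symptoms lasting beyond 24 hours; and
2. ischemia or infarction on imaging; and
3. NIHSS increase of at least 4 and/or mRS increase of more than 2.

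The and/or joins only the two disability measures in condition 3. Condition 2 applies to both.

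| Event | Stroke component | Death component | Counted? |
|---|---|---|---|
| Disabling ischemic stroke | yes | – | yes |
| Hemorrhage with infarction on imaging, disabling | yes | – | yes |
| Fatal intracranial hemorrhage | – | yes | yes |
| Survived disabling hemorrhage, no ischemia or infarction | no (fails 2) | no | **no** |

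The last row is the gap. No separate stroke definition or hemorrhage clause appears elsewhere in the text. Section 9.1 asks the CEC to classify relatedness and seriousness and gives no rule that would widen the endpoint.

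**Step 2: effect of one or two such cases.** The denominator is the 51 implanted subjects planned (safety population, Section 10.6). One case is 1/51 = 1.96 percentage points. With no events, the exact (Clopper-Pearson) upper limit is 1 − 0.025^(1/51) = 6.98%.

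| Events | n = 51: rate (exact 95% CI) | n = 46: rate (exact 95% CI) |
|---|---|---|
| 0 | 0% (0 to 7.0%) | 0% (0 to 7.7%) |
| 1 | 2.0% (0.05 to 10.4%) | 2.2% (0.06 to 11.5%) |
| 2 | 3.9% (0.5 to 13.5%) | 4.3% (0.5 to 14.8%) |

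The column for 46 uses the number expected to have 6-month data.

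**Step 3: how likely such cases are.** The documents give no rate for survived, disabling hemorrhage without infarction. Table 5 supplies no ceiling for the combined class: its five hemorrhage and rupture rows are each below 5%, include events of any severity, and overlap to an unstated degree. The rates p below are therefore assumptions.

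- Expected number = 51p
- P(at least one) = 1 − (1 − p)^51
- P(at least two) = 1 − (1 − p)^51 − 51p(1 − p)^50

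| Assumed p | Expected | P(≥1) | P(≥2) |
|---|---|---|---|
| 0.5% | 0.26 | 23% | 3% |
| 1% | 0.51 | 40% | 9% |
| 2% | 1.02 | 64% | 27% |

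At lower assumed rates of 0.1% and 0.2%, P(≥1) is 1 − 0.999^51 = 5% and 1 − 0.998^51 = 10%.

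**Step 4: can the disability criterion be measured after a bleed?** Up to 6 months, post-baseline NIHSS depends on a diagnosis of stroke. Table 5 lists subarachnoid hemorrhage and rupture in rows apart from CVA, and Section 6.1.1 names hemorrhage beside ischemic stroke. A site might therefore not treat such a bleed as the trigger. The mRS would still be available from scheduled visits, but a case that meets only the NIHSS criterion could be missed. This matters only once hemorrhage is admitted to the definition or counted beside it.

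**The case against.** The strongest reply is that the endpoint is what it says it is: death plus one explicitly defined event, with the definition printed directly beneath it in both places. Nothing says it is meant to cover all severe neurological harm. The study is descriptive and sets no safety threshold. Serious neurologic, device-related and procedure-related events go to the CEC/DSMB (Sections 9.1 and 11.1), and adverse events are tabulated by subject and by event (Section 10.6). Ruptured aneurysms are excluded at entry, and Section 7.9 considers post-placement neurologic change very unlikely, so the true rate may lie well below 0.5%. Amending a primary endpoint is a heavy step if better labelling would do.

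Much of this stands. The safety data are not lost, no decision rule changes, and the rates are only illustrative. It does not close the gap. Tabulating adverse events does not put the event into the headline proportion, and no text prespecifies a count of disabling hemorrhage by the NIHSS and mRS thresholds beside it.

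A second reply is that *major stroke* in Section 10.6 might be read more broadly. It is more likely a dropped word. If it is not, the calculation disagrees with the only definition given, and that also needs correction.

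The points about the NIHSS trigger and CEC recording are secondary. Table 5 also supports reading a bleed as a stroke, the CEC list in Section 9.1 is not stated to be exhaustive, and the case report form content was not available.

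**Conclusion.** The concern holds. On the wording of Sections 2 and 10.4.1, a survived disabling intracranial hemorrhage without ischemia or infarction contributes zero to the primary safety proportion, although the plan lists such bleeds as anticipated. This follows from the text and needs no assumption.

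The size is uncertain. Each case moves the rate by 2.0 percentage points among 51 subjects, but the chance of seeing one depends wholly on an assumed rate: 23% to 64% for 0.5% to 2%, and 5% to 10% for 0.1% to 0.2%. The consequence is a headline safety rate that may understate disabling harm. No test, threshold or sample size changes. It should be fixed because the primary safety measure omits a foreseen severe outcome and the remedy is small.

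**What to change.** **Preferred change.** In the synopsis and Section 10.4.1, widen the imaging condition to *ischemia/infarction or intracranial hemorrhage*, leaving the NIHSS and mRS thresholds as they are. In Section 10.6, restore *disabling* in both places. Report ischemic, hemorrhagic and combined counts.

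**If the sponsor keeps the present definition.** Label the stroke component *ischemic* in the synopsis, Section 10.4.1 and Section 10.6. Prespecify the number of survived disabling intracranial hemorrhages, by the same NIHSS and mRS thresholds, to be shown beside the primary rate.

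**Supporting edits under either option.** State in Section 7.9 and the footnotes to Tables 2 and 8 that the existing post-stroke NIHSS also applies to symptomatic intracranial hemorrhage. State in Section 9.1 that the CEC records stroke type and whether the endpoint definition is met.

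**Cost.** The preferred change amends a primary endpoint. Section 12.2.4 requires amendments to be notified to, or approved by, the ethics committee and regulatory authorities, and does not extend simple notification to endpoint changes. Beyond that, the cost is an occasional extra NIHSS, one CEC field and one table; mRS is already scheduled. The reported safety rate may come out slightly less favorable.

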#### **Primary Performance Endpoint:**

To demonstrate the occlusion rate on the 6 month angiogram as adjudicated by a core laboratory. Success will be defined as complete occlusion demonstrated by a Grade 1 using the Raymond Roy Scale.

Note: In the event of a Grade 2 or more using the Raymond Roy Scale, a second assessment will be made at 12 month follow-up to re-assess for remnant stability or complete occlusion and will be reported as a secondary efficacy endpoint.

### 10.4.2 Independent Analysis of Imaging

Follow-up imaging (i.e., cerebral angiograms) angiographic assessments of the aneurysm shall be completed by an independent core laboratory with experience in neurovascular imaging of IAs.

 Cerus Endovascular	Document Number DNQS428-01	Rev. F	Page 45 of 119
Clinical Investigation Plan	Title		
Confidential & Proprietary	Coil Assisted Flow Diversion: A prospective, single arm, multi-center study to assess the safety and performance of Neqstent in adjunctive therapy (CAFI Study)		

Clinicians responsible for imaging analyses at the core laboratory will not have any financial conflict with the study sponsor and shall not be affiliated with a clinical study site.

## 10.5 Interim Analysis

The sponsor will submit an interim analysis summary of the clinical study's progress (on safety evaluation and device success) to the involved Ethics Committees and Regulatory Authorities after 10 patients are enrolled in the study.

Based on the results following the interim analysis summary, the sample size will be re-evaluated.

## 10.6 Sample Size Rationale and Statistical Considerations

This is a single arm study designed to provide adequate data for the purpose of a pre-market study. It is expected the 51 patients with evaluable data at 6 month and 12 month follow-up (where necessary) will show adequate evidence of safety and performance of Neqstent device.

For the purpose of sample size calculation, the primary outcome measurement is assumed to be the composite of the listed primary endpoint components.

Extensive literature search was conducted to gather information on the non-inferiority margin. Due to limited results found in literature, the non-inferiority margin for this study,  $\delta = 10\%$ , was chosen to align with the study design.

The sample size estimation was based on the following assumption:

- Success rate of the investigational is expected to be 70%
- Success rate of standard treatment is estimated to be 55%
- Power is set at 80% and one-sided significance level is set at 5%
- Expected rate of attrition is 10%

Based on the assumptions, a total of 46 subjects are required to show that the expected success rate of 70% is different than the true rate of 55% with a delta of 10%. Adding in additional subjects for anticipated loss to follow-up, 51 subjects are needed to be enrolled for a total of 46 subjects with 6 month data.

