#### **Endpoint Analysis:**

The primary performance endpoint will be calculated as the proportion of subjects with complete occlusion demonstrated with a Grade 1 on the Raymond Roy Scale at 6 months follow-up. In the event of a Grade 2 or more using the Raymond Roy Scale, a second assessment will be made at 12- month follow-up to re-assess for complete occlusion and will be reported as a secondary efficacy.

For AE reporting, both subject counts and event counts will be presented in tabular summaries of results.

A summary of subjects with protocol deviations will be reported but those subjects will be included in all analyses although endpoints may be summarized without the subjects (per-protocol analysis group) to provide additional information but not for the primary analysis.

For continuous variables, statistics will include means, standard deviations, medians and ranges. Categorical variables will be summarized in frequency distributions. Missing data will not be imputed. The number of data values available for each analysis will be reported so that the impact of missing data can be seen.

Statistical analyses will be conducted in SAS version 9.4 or above (SAS Institute, Cary, N.C.).

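### Section 10.6 sizes the trial on a composite that is never defined or analysed, so the plan does not say which endpoint the 70% and 55% rates and the 80% power belong to.

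*Combined protocol and SAP*

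**What the plan says.** Section 10.6 opens its sample size argument by saying that "the primary outcome measurement is assumed to be the composite of the listed primary endpoint components". It then lists its inputs, the rates being percentages. For the device it gives "Success rate of the investigational is expected to be 70". The comparator is described by "Success rate of standard treatment is estimated to be 55". The error rates follow as "Power is set at 80% and one-sided significance level is set at 5", and the allowance for dropout reads "Expected rate of attrition is 10". It concludes that 46 subjects are needed to show that the expected rate is "different than the true rate of 55% with a delta of 10" (per cent), and that "51 subjects are needed to be enrolled for a total of 46 subjects with 6 month data".

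The endpoints themselves are set out differently. The synopsis and section 10.4.1 list two primary endpoints:

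- a safety proportion, covering non-accidental death or major disabling stroke to 30 days and then major disabling stroke or neurological death to 6 months;
- a performance proportion, Raymond Roy Grade 1 at 6 months as judged by the core laboratory.

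Success is defined only under the second. The analysis text in section 10.6 keeps them apart. The safety endpoint is one proportion. For performance, "The primary performance endpoint will be calculated as the proportion of subjects with complete occlusion demonstrated with a Grade 1", with the 6-month visit as the timepoint.

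The opening of section 10 says that the study is not powered for statistical significance, and section 10.1 calls it descriptive.

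**The concern.** A sample size statement is informative only if its rates belong to an outcome that will be estimated. Here the sizing sentence points to an outcome that combines safety and performance, while the endpoint and analysis sections report each separately and give no rule for combining them. The 70% and 55% have no stated source, so their endpoint cannot be recovered that way either.

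Two uses of the plan suffer. A reader of the final report cannot tell whether the observed Grade 1 rate should be set against 70%. Section 10.5 also says that the sample size will be re-evaluated after the interim summary on 10 patients, which requires knowing which outcome the 70% describes. As the text stands, either reading could be adopted after the data are seen.

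**Working it through.** **1. Reproduce 46.** Inputs from section 10.6: control rate 0.55, device rate 0.70, margin 0.10, one-sided 5%, power 80%. The section states no formula. The usual two-arm non-inferiority formula, per arm, is

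n = (z₀.₉₅ + z₀.₈₀)² × [p_c(1−p_c) + p_t(1−p_t)] / (p_t − p_c + margin)²

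= 6.183 × (0.2475 + 0.2100) / 0.25² = 45.26, rounded up to 46.

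This matches, so I infer that it was the method used. One-sample normal formulas with null and alternative variances do not match: 70% against 55% needs 65, and 70% against 45% (55% minus 10%) needs 24. For attrition, 46 × 1.10 = 50.6, which gives 51.

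**2. Look for the composite.**

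| Place | Outcome |
|---|---|
| Synopsis; 10.4.1 | Two separate primary endpoints; success means Grade 1 occlusion |
| 10.6, sizing | One composite with success rates of 70% and 55% |
| 10.6, analysis | Two separate proportions; no combined outcome |

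**3. Size the ambiguity.** The documents give no composite rate and no expected rate for the primary safety endpoint. I assume a 6-month event rate s of 2%, 5% or 10%, independent of occlusion, and define composite success as Grade 1 with no safety event. The formula of step 1 is used throughout.

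*Reading A: 70% is the occlusion rate.* Composite success is 0.70 × (1 − s).

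| s | Composite success | n per arm, comparator fixed at 55% | Comparator 0.55 × (1 − s) | n per arm, both lowered |
|---|---|---|---|---|
| 2% | 68.6% | 52 | 53.9% | 48 |
| 5% | 66.5% | 63 | 52.3% | 50 |
| 10% | 63.0% | 92 | 49.5% | 55 |

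Worked example for s = 5%, comparator fixed: 6.183 × (0.2475 + 0.2228) / 0.215² = 62.9, so 63. With both lowered: 6.183 × (0.2495 + 0.2228) / 0.2425² = 49.7, so 50. On the same formula, power at 46 per arm is 80.6% at the plan's own rates. It becomes 76.0%, 68.5% and 54.6% with the comparator fixed, and 79.2%, 77.3% and 74.2% with both lowered.

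*Reading B: 70% is the composite rate.* Implied occlusion is 0.70 / (1 − s) = 71.4%, 73.7% and 77.8%. Against 55%, n per arm is 40, 34 and 25. If 55% is also a composite rate, the comparator rises in the same way, to 56.1%, 57.9% and 61.1%, and n is 44, 41 and 36. For s = 5%: 6.183 × (0.2438 + 0.1939) / 0.2579² = 40.7, so 41.

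**4. What 46 patients give in a single arm for occlusion.** Exact one-sided 5% binomial test, true rate 70%:

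- Null 55%: at least 32 successes needed, exact alpha 3.2%, power 59.7%.
- Null 45%: at least 27 successes needed, exact alpha 4.3%, power 96.4%.

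Neither is 80%. For precision, 1.96 × √(0.70 × 0.30 / 46) = 0.132, or about ±13 points. The exact 95% interval for 32 of 46 is 54.2% to 82.3%.

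**The case against.** The strongest reply is that one sentence is badly worded and the rates are simply occlusion rates. Grade 1 is the only success the plan defines, and the sizing paragraph ends on 6-month data, which is the occlusion timepoint. The complete-occlusion rates cited in the background are of the same order: above 50% at 6 months for flow diverters, and 67%, 58% and 44% in series of another intrasaccular device. I accept this as the likeliest reading, but the documents do not confirm it, and the sentence as written says otherwise.

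A reader might infer something stronger: that the 70% and 55% rates are wrong for the reported endpoint, that the calculation is optimistic, and that up to 92 per arm are needed. The documents do not support that. The 92 needs a 10% event rate, while Table 5 puts ischaemic and haemorrhagic stroke each below 5% and section 7.9 expects neurological change to be very unlikely. It also lowers the device rate for safety events while leaving the comparator untouched. With both lowered the size moves only to 48 to 55, and under Reading B the plan is conservative for occlusion.

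Another benign reading is that the composite means only the death-or-stroke safety endpoint. That fails: 70% and 55% success would imply event rates of 30% and 45%, far from Table 5.

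Finally, section 10 says that the study is not powered, and the synopsis ties 51 to the notified-body obligation. This limits the consequence, since no planned test uses the 80%. It does not remove the inconsistency, because section 10.6 still derives 46 and 51 from a power claim.

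**Conclusion.** The point holds as an internal inconsistency. Section 10.6 ties its rates and its power to a composite that the plan neither defines nor reports, and nothing in the documents says which reported endpoint was meant. It does not show that the trial is too small.

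The direction and size of the effect depend on the reading: 48 to 92 per arm in place of 46 if 70% is occlusion and a composite is intended (the upper part only with a fixed 55% comparator), or 25 to 44 if 70% is the composite and occlusion is intended. If both rates are occlusion rates and occlusion is the sizing endpoint, the 46 is unaffected by this point. These ranges rest on an assumed independent 2% to 10% safety-event rate and on a two-arm formula inferred from its match to 46.

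A separate problem bears on the repair. The 46 is a per-arm figure for a two-arm comparison, used in a single-arm study, so naming the endpoint alone would not make the 80% correct. Both primary endpoints will still be reported; what is lost is a usable justification for the sample size.

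**What to change.** In section 10.6, replace the composite sentence with: *The sample size is based on the primary performance endpoint (Raymond Roy Grade 1 at 6 months, core laboratory).* Give the source of the 70% and 55% for that endpoint.

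Then replace the 80% power claim in one of two ways:

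- State the single-arm power at 46 patients for a true rate of 70% with an exact one-sided 5% test (about 60% against 55%, or about 96% against 45%), and name the reference rate chosen.
- State the precision instead (95% confidence interval of about ±13 points at an observed 70%). This fits better with the opening of section 10.

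Report the primary safety proportion with its exact confidence interval. If a composite is truly intended, define it in section 10.4.1 (Grade 1 at 6 months with no primary safety event), add it to the analysis, and justify its rates.

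The cost is a few sentences, with no added patients or data. The drawback is that the stated power becomes less favourable against 55%, or is dropped. Keeping 80% against 55% in a single arm would need more than 46 evaluable patients (65 by the one-sample formula).
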